5.8.1.2. Handling of Missing and/or Unquantifiable Immune Response Data

Missing immune response data will not be imputed.

Values below the lower limit of quantification (LLOQ) or limit of detection (LOD, if available instead of LLOQ) will be handled as follows:

- Calculation of geometric mean and median:
 - values <LLOQ are imputed with LLOQ/2.
- Calculation of fold increases from baseline:
 - values <LLOQ are imputed with LLOQ.

Values above the upper limit of quantification (ULOQ) will be handled as follows:

- Calculation of geommean and median:
 - Values >ULOQ are imputed with ULOQ.
- Calculation of fold increases from baseline:
 - Values >ULOQ are imputed with ULOQ.

5.8.1.3. Handling of Changes in Assay Status Throughout the Study Conduct

In case of changes in assay status, from “qualified” to “validated”, the LLOQ and ULOQ are likely to change as well. If this should happen, then the SDTM database will contain records pertaining to the assay in the qualified status and records pertaining to the validated status, and the LLOQ and ULOQ values will also differ.

The statistical analysis will use the LLOQ and ULOQ values associated with the validated assay and will retrospectively apply these on all the data pertaining to the assay, including the data obtained while the assay status was “qualified”. This may imply that data received, statistically analyzed, and presented at an earlier time may change. Graphical displays will show the eventually used LLOQ and ULOQ values. Graphs and tables will have an additional footnote, that reflects the assay status.

5.8.1.4. Immunogenicity Against the Insert

5.8.1.4.1. Humoral assays

The seroresponse rate of S-ELISA (or equivalent assay, e.g. MSD), and the VNA will be reported as the proportion of participants with either:

- a baseline sample value of less than or equal to the lower limit of quantitation (LLOQ; [\leq LLOQ]) and a postbaseline sample strictly greater than the LLOQ ($>$ LLOQ), or
- a baseline sample value strictly greater than the LLOQ ($>$ LLOQ) and a postbaseline sample value representing an at least 4-fold (\geq 4-fold) increase from the baseline sample value.

In addition, the following definition of seroresponse rate of the VNA (and possibly S-ELISA or equivalent assay e.g. MSD) will be reported as an exploratory endpoint: the proportion of participants with at least 4-fold increase from the baseline sample value, where a baseline sample value of less than or equal to the lower limit of quantitation will be set to LLOQ for the analysis.

For S-ELISA and VNA (both wild-type virus and pseudovirion expressing S protein, as available) assays, the following results will be calculated: N, geometric mean and corresponding 95% CI of

the actual values and fold increases from baseline and from pre-dose 2 or pre-dose 3 (for time points after dose 2 and time points post booster, respectively) will be tabulated and graphically presented.

For the calculation of the geometric mean and its corresponding 95% CI, the arithmetic mean and its corresponding 95% CI are calculated on the \log_{10} transformed values. These values are back transformed to provide the geometric mean and its corresponding 95% CI.

Actual values are tabulated and shown as dot plots with dots for participant values, and the corresponding geometric mean and 95% CI per time point for each assay. In addition, GMT (VNA) or GMC (S-ELISA or equivalent assay, e.g. MSD) plots over time, combining the regimens in one graph (without individual participant dots) will also be generated.

Participant profiles of the actual values over time will be graphically presented. In the graphs, original values will be displayed on the \log_{10} scale. Reverse distribution curves of the actual values will be provided for selected time points. Further details and/or updated rules will be provided in the DPS.

The ratio of binding antibodies (S-ELISA or equivalent assay, e.g. MSD) to wild type VNA, and the ratio of binding antibodies (S-ELISA or equivalent assay, e.g. MSD) to pseudovirion expressing S protein VNA will be calculated for each time point. Values <LLOQ will be imputed with LLOQ for the calculation of the ratios. In addition, the ratio of the fold increase from baseline in binding antibodies (S-ELISA or equivalent assay, e.g. MSD) to the fold increase from baseline in wild type VNA, and the ratio of the fold increase from baseline in binding antibodies (S-ELISA or equivalent assay, e.g. MSD) to the fold increase from baseline in pseudovirion expressing S protein VNA will be calculated for each post-baseline time point. Values <LLOQ will be imputed with LLOQ for the calculation of the fold increase ratios. The following statistics will be calculated and tabulated: N, geometric mean and corresponding 95% CI of the ratio. Graphical displays will also be prepared, showing – for each time point – the geometric mean of the ratio and its 95% CI, together with the individual data points (dot plot).

If a similar assay is performed at different analyzing labs, then separate statistical analyses may be performed.

Scatterplots between humoral assay results will be provided for selected time points. These may include but are not limited to:

- Binding antibodies S-ELISA (or equivalent assay) versus VNA (wtVNA and/or psVNA)
- Ad26 VNA versus S-ELISA (or equivalent assay), wtVNA or psVNA (as available)

If a similar assay is performed at different analyzing labs, then the statistical analyses may distinguish between these and provide separate scatterplots for each analyzing lab versus the other assay of interest. These scatterplots will display the values as analyzed for the geometric mean calculations, with values <LLOQ imputed with LLOQ (if an LLOQ is defined) and values >ULOQ imputed with ULOQ (if an ULOQ is defined). The LLOQ and ULOQ cut-off values per assay will

be visualized in the scatterplots. Spearman correlation coefficients will also be provided (one per scatterplot).

Further details and/or updated rules will be provided in the DPS.

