
 To assess the safety and reactogenicity of Ad26.COV2.S administered IM as a booster in adolescent participants (Groups 1-3). 	
 Solicited local and systemic AEs for 7 days post-booster. Unsolicited AEs for 28 days post-booster. MAAEs from the booster until 6 months post-vaccination.

 To evaluate the humoral immune response in adolescent participants who receive a booster dose during the study, pre-boost and at selected time points post booster vaccination (Groups 1-3). 	
 Serological response to vaccination measured by binding (S-ELISA and/or equivalent assay) and/or neutralizing (VNA) antibody titers

Exploratory	

 To examine the immune response in vaccinated adolescents after SARS-CoV-2 infection. 	
 Confirmation of SARS-CoV-2 infection by molecular testing.⁽¹⁾ SARS-CoV-2 neutralizing titers in serum measured by a VNA.⁽¹⁾ SARS-CoV-2-binding antibodies measured by ELISA (or equivalent assay): Analysis of antibodies binding to the SARS-CoV-2 S and/or N protein.⁽¹⁾ Analysis of gene expression by ribonucleic acid (RNA) transcript profiling in adolescents.⁽¹⁾

 To assess the correlation between the binding antibodies (S-ELISA) and neutralizing antibody (VNA) titers to SARS-CoV-2 at selected timepoints. 	
 Correlation between ELISA (S-ELISA; EU/mL, or equivalent assay) and VNA (wtVNA⁽¹⁾ and/or psVNA) titers at selected timepoints.

 To assess the occurrence of symptomatic molecularly confirmed COVID-19 and severity of COVID-19 signs and symptoms in adolescents. 	
 The number of adolescents with molecularly confirmed COVID-19.⁽¹⁾ Presence and severity of COVID-19 signs and symptoms as measured by the Symptoms of Infection with Coronavirus-19 (SIC).

 To assess for the occurrence of asymptomatic SARS-CoV-2 infection. For Asymptomatic case definition: See CTP Section 10.9.3 	
 Serologic conversion between baseline (Day 1; pre-vaccination) and selected timepoints post-vaccination using an ELISA and/or SARS-CoV-2 immunoglobulin assay that is dependent on the SARS-CoV-2 N protein The number of asymptomatic participants with a SARS-CoV-2 positive molecular test.

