5. STATISTICAL ANALYSES

5.1. General Considerations

Details of the vaccine schedules associated to the primary vaccine regimen will be provided in the data presentation specification (DPS) document. Vaccination schedule have 2 components:

- Primary Vaccine Regimen (1-active dose or 2-active dose)
- Booster Vaccination (i.e. after unblinding)

Unless specified otherwise, analyses outputs will be produced by age group (12 to 15, 16 to 17, and overall). Where applicable, output will include results by dose level (1-active dose regimen and 2-active dose regimen combined) to report the post-dose 1 period.

All safety and immunogenicity data after a participant has received any other SARS-CoV-2 vaccine not part of the protocol will not be tabulated. Those data will be in listings.

A baseline (or reference) value will be defined as the value of the last available assessment prior to the first vaccination on Day 1, unless specified otherwise.

Unless otherwise stated, safety analyses will be conducted on the FAS, Immunogenicity analyses on the PPI.

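### In Groups 1-3 the post-booster seroresponse rate is cumulative since Day 1, and no planned measure gives the proportion who responded to the booster itself

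*SAP*

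**What the plan says.** SAP 5.1 gives the general rule: "A baseline (or reference) value will be defined as the value of the last available assessment prior to the first vaccination on Day 1", unless another reference is specified.

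SAP 5.8.1.4.1 then defines seroresponse in two ways.

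- **Main definition.** Either the participant has "a baseline sample value of less than or equal to the lower limit of quantitation" and a later sample above it, or starts above the LLOQ and has "a postbaseline sample value representing an at least 4-fold" increase from baseline.
- **Exploratory definition.** This is "the proportion of participants with at least 4-fold increase from the baseline sample value", with baseline values at or below the LLOQ set to the LLOQ.

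Neither definition names a different reference for samples taken after the booster. SAP 5.4.3 and 5.8.1 present immunogenicity results by scheduled time point, which includes the post-booster visits.

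For geometric means the same section goes further. It tabulates and plots "fold increases from baseline and from pre-dose 2 or pre-dose 3 (for time points after dose 2 and time points post booster, respectively"). Fold increases therefore have two references, and the seroresponse rate has one.

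The booster response is a secondary objective in SAP 1.1. It covers Groups 1-3 before the booster and at selected times after it.

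**The concern.** Groups 1-3 all receive active vaccine on Day 1 and a booster from about Day 184. Suppose a participant met the criterion after the first dose and still meets it just before the booster. That participant is counted as a seroresponder at every post-booster visit on which the titre holds, even if the booster changed nothing. A table row labelled as seroresponse after the booster invites the reader to credit the booster with responses to the first dose.

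The design cannot correct for this. Every one-dose group is scheduled for the booster and Groups 4-6 receive none (SAP 1.2), so no randomized unboosted one-dose group shows what the Day 1-based rate would have been without it. At stake is a clear answer, on the responder scale, to the booster secondary objective.

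**Working it through.** The plan states no expected rate or precision for post-booster seroresponse, so there is no figure of its own to reproduce. The check applies the SAP rule to a booster with no effect.

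**Inputs from the documents.** Baseline is before dose 1 (SAP 5.1). The seroresponse rules are those of SAP 5.8.1.4.1. Each group has about 50 participants (SAP 1.2). A Day 184 sample exists in Groups 1-3, windowed against vaccination 1 (SAP 6.3), and samples planned for a vaccination day must be taken before the injection (SAP 5.1.4). SAP 2 says that many participants were seropositive at baseline on central testing but gives no percentage.

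**Assumptions, none from the documents.**
- Let m be the Day 184 geometric mean as a multiple of the LLOQ in baseline-negatives, and the same multiple of own baseline in baseline-positives: 1, 2, 4, 8 or 16.
- The between-participant SD on the log10 scale is 0.4 or 0.6, and the assay SD is 0.10 or 0.15.
- The share p seropositive at baseline is 0, 30 or 60%.
- The true titre is the same before and after the booster.

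**Formula.** Let s = √(between SD² + assay SD²). The main-definition rate at Day 184 is

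(1 − p)·Φ(log10 m / s) + p·Φ((log10 m − log10 4) / s).

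With an inert booster the post-booster titres have the same distribution, so the post-booster rate is the same number.

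**Worked cases, with SDs 0.4 and 0.10.** s = √(0.16 + 0.01) = 0.412, and log10 4 = 0.602.
- p = 0, m = 4: Φ(0.602/0.412) = Φ(1.46) = 0.928.
- p = 0.3, m = 4: 0.7 × 0.928 + 0.3 × 0.5 = 0.800.
- p = 0.6, m = 1: 0.4 × 0.5 + 0.6 × Φ(−1.46) = 0.200 + 0.6 × 0.072 = 0.243.

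A simulation of 200,000 participants per scenario gives 0.928, 0.801 and 0.244 for these cases. Across all scenarios, the rates before and after the inert booster agree to within 0.2 percentage points.

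**Seroresponse reported after an inert booster, Day 1 anchor (range over the SDs).**

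| Definition | p | m = 1 | m = 2 | m = 4 | m = 8 | m = 16 |
|---|---|---|---|---|---|---|
| Main | 0% | 50% | 69–77% | 84–93% | 93–99% | 97–99.8% |
| Main | 30% | 37–40% | 58–61% | 74–80% | 86–92% | 93–98% |
| Main | 60% | 24–30% | 45–46% | 63–67% | 78–86% | 89–96% |
| Exploratory | any | 7–17% | 23–32% | 50% | 69–77% | 84–93% |

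**Same scenarios, pre-dose 3 anchor.** The two-part main rule gives about 0 to 8%. What remains is assay noise around the LLOQ. A rule requiring only a 4-fold rise gives 0.3% or less.

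**What one group's table would show.** If 40 of 50 already met the Day 1-based criterion at Day 184, an inert booster would be reported as 80% seroresponse (exact 95% interval 66.3 to 90.0%). A real booster could add at most 100 − 80 = 20 points.

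**The case against.** The other side has a good deal to say.

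- **The booster effect is already measured.** The geometric mean fold increase from pre-dose 3, with its 95% interval, would be about 1 for an inert booster. Titres by time point, individual profiles and reverse distribution curves are also planned. This stands. A reader might infer that the plan cannot tell a working booster from an inert one, and the documents do not support that.
- **The Day 184 rate should appear in the same output.** Results are given by time point and the objective includes the pre-boost sample, so equal rates before and after would be visible. This largely stands, although the SAP does not ask for the two to be set side by side. The difference between two cumulative rates also misses anyone who already met the criterion and then rose again.
- **A high rate is not certain.** A reader might infer that the measure must sit near its ceiling. That depends on unquantified persistence and seropositivity, and the table runs down to 24% under the main definition.
- **The references do not conflict.** A reader might infer that fold increases move from the Day 1 reference to pre-dose 3. The SAP tabulates both, so the gap is only that the second reference is not carried over to the responder rate.
- **The Day 1 anchor has a use.** It gives one scale for the whole series and for cumulative comparison with Groups 4-6. This stands and is a reason to keep it.
- **More rules may exist elsewhere.** SAP 5.8.1.4.1 defers details to the Data Presentation Specifications, which are not among the documents, and SAP 1.1 allows for different responder definitions. However, the two definitions that the SAP writes out both use Day 1.

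None of this supplies the proportion who responded to the booster. A mean fold rise does not give it.

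**Conclusion.** The point holds in a limited form. As written, the post-booster seroresponse rate in Groups 1-3 measures response since Day 1, not response to the booster. With an inert booster it would equal the Day 184 rate apart from assay noise. That identity follows from the definitions and needs no assumption about titres. The size of the rate does rest on assumptions: about 24% to over 95% under the main definition in the scenarios above, against about 0 to 8% with a pre-dose 3 anchor.

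The consequence is modest. The analysis is descriptive, with no hypothesis test (SAP 2). The dose-selection data stop at 28 days after dose 2 (SAP 5.9), before the booster is given. This is a cheap improvement to a secondary analysis, and the existing rate is not invalid.

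**What to change.** In SAP 5.8.1.4.1, for post-booster time points in Groups 1-3:

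1. Add a seroresponse rate anchored on the pre-dose 3 sample. A responder has a pre-booster value at or below the LLOQ and a post-booster value above it, or a pre-booster value above the LLOQ and at least a 4-fold rise from it.
2. Keep the Day 1-based rate, label it 'cumulative seroresponse since Day 1', and show it beside the Day 184 pre-booster rate.

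The cost is SAP wording, one derived flag and one extra table. The sample is already collected and its value is already used for fold increases. The pre-dose 3 rate will be lower than the cumulative rate. It will also be harder to reach for participants with high pre-booster titres or with values near the ULOQ, since SAP 5.8.1.2 caps values there. A footnote should say so, because better-primed groups could otherwise look like poorer booster responders.

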5.8.2. COVID-19 Case Monitoring to Detect Imbalances Across Study Groups (Harm Monitoring)

In the absence of a placebo arm, no 'harm monitoring' can be conducted.

5.8.3. COVID-19-like Signs and Symptoms

Procedures to be performed in the event a participant experiences signs or symptoms suggesting possible COVID-19 are detailed in CTP Section 1.3, Schedule of Activities and CTP Section 8.1.2, Procedures in case of COVID-19-like Signs and Symptoms.

The COVID-19-like Signs and Symptoms will be analyses for the participants with a COVID-19 infection. The presence of SARS-CoV-2 infection will be assessed at the study site by molecular testing using the nasal swab sample and also based on SARS-CoV-2 N serology results. It is defined as a SARS-CoV-2 N serology (N-ELISA) change from baseline result from negative to positive, or a positive SARS-CoV-2 PCR-status.

The analyses described in this section will be conducted on the FAS at the time of the final analysis.

The number and percentage of participants with at least one SARS-CoV-2 infection will be tabulated by vaccination schedule.

In the group of participants seronegative at baseline, the number and percentage of participants with at least one positive non-S protein ELISA (e.g., N ELISA), if available, will be tabulated by vaccination schedule.

For each participant with confirmed COVID-19 infection, a narrative will be prepared based on the visit performed 28 days after the onset of COVID-19 signs and symptoms and other selected information from the clinical database, as available:

- participant ID
- vaccination regimen
- sex, race, ethnicity, age, BMI, dates at which vaccinations were received
- pulse oximetry
- physical examination findings based on the visit performed 28 days after the onset of COVID-19 signs and symptoms
- vital signs including body temperature based on the visit performed 28 days after the onset of COVID-19 signs and symptoms
- Humoral immune responses as collected at the planned time points + those obtained from the blood sample taken on the visits performed 3 and 28 days after the onset of COVID-19 signs and symptoms. This information may be presented graphically.

For the analysis of the SIC (Patient Reported Outcomes, PRO) data, the following considerations apply:

- An “episode” is defined as a period in which any symptoms are reported on the SIC, starting from the first day on which symptoms were reported until the first day that the PRO was not completed because the symptoms had resolved (this will be indicated in the SDTM data, with reason for not completing the PRO = “Symptoms resolved” (or similar) or death)
- A symptom (e.g. feeling generally unwell, fatigue, physical weakness, cough, etc.) is assumed to be present on each day the associated Yes/No question is answered “Yes” or the associated severity question has a rating > 0 .
- If the PRO was not completed due to the participant being too ill or due to the participant being hospitalized, the symptom will be considered present with maximum severity score. If the PRO was completed due to any other reason, no imputations will be done.

Duration of the episode will be calculated as (episode end date – episode start date) + 1. Duration of each symptom will be calculated as last date of symptom reporting – its first date + 1.

The following analyses will be conducted for confirmed SARS-CoV-2 infection cases:

- At the level of first episodes, the following statistics will be calculated: number of episodes, mean and median duration of episodes (with min, max, q1 and q3), and mean and median number of symptoms reported per episode (with min, max, q1 and q3).
- At the level of the symptoms for each first episode, the following statistics will be calculated: number of participants experiencing the symptom, mean and median duration of each symptom (with min, max, q1 and q3), median (with min, max, q1 and q3) of highest severity of each symptom, median duration of the highest severity of each symptom (with min, max, q1 and q3).
- At the level of the participants, for each episode and each symptom separately, the duration, and minimum and maximum severity scores will be tabulated (as available).

In addition, participant listings will be provided containing the SIC information for each time point. Details about these analyses will be provided in the DPS.

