2. STATISTICAL HYPOTHESES

There is no formal hypothesis testing in Part 1.

Descriptive statistics will be reported to descriptively compare vaccine immunogenicity in adolescents from this study VAC31518COV3006 versus vaccine immunogenicity in selected young adults (18 to 25 years of age) from study VAC31518COV3001 or study VAC31518COV3009 (with similar baseline characteristics to the participants expected to be enrolled in this study – see Section 6.11), and between study groups in VAC31518COV3006.

All enrolled participants were seronegative for SARS-CoV-2 antibodies when screened with local rapid finger-prick serology testing at baseline. However, the primary analysis results have shown that many participants were retrospectively established to be SARS-CoV-2 seropositive at baseline by central testing with Nucleocapsid (N) and/or Spike (S) -based serology. Therefore data from SARS-CoV-2 seropositive young adult (18 to 25 years of age) selected from other Phase 3 studies will be used to compare vaccine immunogenicity in seropositive at baseline adolescents from this study.

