5.6. Exploratory Endpoint(s) Analysis

Definitions and details about the analysis methods for exploratory humoral immunogenicity endpoints are given in Section [5.8.1](#). Some of the exploratory immunogenicity endpoints mentioned in this section will only be considered as potential assessment for post-hoc analysis after the primary analysis is performed, as described in Section [1.1](#).

Immune response in vaccinated adolescents after natural SARS-CoV-2 infection.

- Confirmation of SARS-CoV-2 infection by molecular testing.
- SARS-CoV-2 neutralizing titers in serum measured by a VNA.
- SARS-CoV-2-binding antibodies measured by ELISA: Analysis of antibodies binding to the SARS-CoV-2 S and/or N-protein. Infections in this study were identified either by a positive PCR test or by N serology seroconversion (N-ELISA result from negative to positive) [see Section [5.8.3](#)]. In order to censor data from participants following a potential SARS-CoV-2 infection not identified by the pre-defined infection rule, a sensitivity analysis will be performed on vaccine-induced humoral responses (binding and neutralizing antibody titers) for the PPI at the time of the final analysis. In this sensitivity analysis, data from participants from the time point where a ≥ 2 -fold increase in N-ELISA titers is observed in any two consecutive available time points during the study will be censored.

Correlation (at selected timepoints)

- ELISA (S-ELISA; EU/mL, or equivalent assay) and VNA (wtVNA and/or psVNA) titers
 - For S-ELISA and wtVNA correlation.
 - For S-ELISA and psVNA correlation.
- ELISA (S-ELISA; EU/mL, or equivalent assay) titers at baseline and its fold increase from baseline.

Occurrence of symptomatic molecularly confirmed COVID-19 and severity of COVID-19 signs and symptoms in adolescents

- The number of adolescents with molecularly confirmed COVID-19.
- Presence and severity of COVID-19 signs and symptoms as measured by the Symptoms of Infection with Coronavirus-19 (SIC).

Occurrence of asymptomatic SARS-CoV-2 infection

- Serologic conversion between baseline (Day 1; pre-vaccination) and selected timepoints post-vaccination using an ELISA and/or SARS-CoV-2 immunoglobulin assay that is dependent on the SARS-CoV-2 N protein
- The number of asymptomatic participants with a SARS-CoV-2 positive molecular test.

For asymptomatic case definition, see CTP (Section 10.9.3).

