6.3. Appendix 3 The Per Protocol Immunogenicity population

The Per Protocol Immunogenicity population will include all randomized and vaccinated participants for whom immunogenicity data are available excluding participants with major protocol deviations expected to impact the immunogenicity outcomes and occurring on Day 1 or before.

In addition, samples obtained from participants will be excluded from the analysis set:

- a- after major protocol deviations expected to impact the immunogenicity outcomes and occurring after Day 1,
- b- after missed vaccinations,
- c- on or after natural SARS-CoV-2 infection (if confirmed by molecular testing or non-S-ELISA [or equivalent assay]) occurring during the study after randomization (if applicable),
- d- after other SARS-CoV-2 vaccination outside the study, or
- e- outside pre-defined time windows (Section 5.1.4).

In terms of derivation, the samples to consider for analysis on Per Protocol Immunogenicity must meet the following criteria:

Subject level

- **Crit1:** Must be randomized
- **Crit2:** Must be in FAS

- **Crit7:** No major protocol deviations with impact on immunogenicity on or before day 1 excluding Deviation Categories '85 for sample not in window', '87 for sample not stored properly'

Subject data level

Subject data to be excluded on and after the date of any of the following events:

- **Crit11:** seropositive post-Baseline by N-ELISA (value>LLOQ), if seronegative at baseline (as defined in Section [5.8.4](#))
- **Crit13:** SARS-CoV-2 infection occurring on or after Day 1
- **Crit20:** Major protocol deviations with impact on immunogenicity after day 1 except for deviation categories '85' or '87', which includes
 - **Crit21:** post SARS-CoV-2 viral vaccination outside the study occurring after Day 1
 - **Crit22:** Vacc 2 not in D57 +/- 8 days
 - **Crit23:** no Vacc 2, then exclude samples where the sample date>Day57+8.
 - **Crit24:** Vacc 3 not in D184 +180/-30 days post vacc1 – Groups 1, 2, 3
 - **Crit25:** no Vacc 3 (within 180 days post Day 184), then exclude samples where the sample date>Day184+30 – Groups 1, 2, 3

Vacc 2 refers to the 2nd dose of the primary regimen

Vacc 3 refers to booster

Sample level

Samples to be excluded on the date of deviation for '85' or '87' events:

- Crit30: major protocol deviations with impact on immunogenicity deviation categories '85' or '87', that is
 - **Crit31:** D1 sample not in window
 - **Crit32:** D29 sample not in window

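### Crude infection percentages by vaccination schedule cover about 12 months in Groups 1-3 and about 8 months in Groups 4-6, so they cannot be compared between those two sets of groups

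*SAP*

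**What the plan says.** SAP 5.8.3 gives the infection rule: "It is defined as a SARS-CoV-2 N serology (N-ELISA) change from baseline result from negative to positive, or a positive SARS-CoV-2 PCR-status". On timing and analysis set it says: "The analyses described in this section will be conducted on the FAS at the time of the final analysis". The summary measure is a count and a percentage: "The number and percentage of participants with at least one SARS-CoV-2 infection will be tabulated by vaccination schedule". The rule in SAP 5.1.2 to present results by phase or period is stated for safety results, and nothing in 5.8.3 extends it to this table.

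Protocol 4.1 (Study Duration) gives about 12 months for Groups 1-3 and about 8 months for Groups 4-6. The schedules of activities put the last visit at Day 366 ±21 (protocol 1.3.1) and Day 240 ±21 (protocol 1.3.2). Groups 1-3 also receive a booster at Day 184.

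On serostatus, SAP 2 reports that "many participants were retrospectively established to be SARS-CoV-2 seropositive at baseline by central testing with Nucleocapsid (N) and/or Spike (S) -based serology". SAP 5.8.4 calls a participant seronegative only if negative on both S-ELISA and N-ELISA. Two rules rest on that definition. One is a companion table in 5.8.3: "In the group of participants seronegative at baseline, the number and percentage of participants with at least one positive non-S protein ELISA", again by schedule. The other is Crit11 in SAP 6.3 (Appendix 3), which excludes data once a participant is "seropositive post-Baseline by N-ELISA (value>LLOQ), if seronegative at baseline".

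**The concern.** A cumulative percentage grows with time under observation. One set of groups is watched for roughly half as long again as the other, so the same underlying risk will show as more infections in the one-dose-plus-booster groups. Detection effort differs in the same direction. As far as the broken tables can be read, Groups 1-3 have post-baseline serum at Days 29, 57, 71, 184, 198 and 366 and a central nasal swab at Day 184, while Groups 4-6 have serum at Days 29, 57, 71 and 240. The extra months in Groups 1-3 also follow a booster that the other groups do not receive. The trial has no placebo arm, so a reader of this table has only the schedules to compare.

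There is a second, separate issue of level. A participant N-positive at baseline cannot change from negative to positive, yet stays in the FAS denominator. Conversely, an S-positive, N-negative participant can convert but is left out of the companion table, because that table requires both assays to be negative.

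**Working it through.** **1. Follow-up, from the schedules of activities.** Groups 1-3: (366 - 1)/30.44 = 11.99 months. Groups 4-6: (240 - 1)/30.44 = 7.85 months. These reproduce the protocol's 12 and 8 months. The ratio is 365/239 = 1.53.

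**2. Effect on the crude percentage.** Assume the same constant hazard in all groups, complete follow-up and equal detection. If p is the risk by Day 240, the risk by Day 366 is 1 - (1 - p)^(365/239). The documents state no infection rate, so p is varied:

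| Risk by Day 240 | Risk by Day 366 | Difference (points) | Ratio |
|---|---|---|---|
| 5% | 7.5% | 2.5 | 1.51 |
| 15% | 22.0% | 7.0 | 1.47 |
| 20% | 28.9% | 8.9 | 1.44 |
| 30% | 42.0% | 12.0 | 1.40 |
| 50% | 65.3% | 15.3 | 1.31 |

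As a gauge only, since no test is planned: with 150 v 150 participants, a gap of this kind would look nominally significant (two-sided 5%) in about 15% of trials at p = 5% and about 77% at p = 50%.

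**3. What a rate does.** At p = 20%, the rate in Groups 4-6 is -ln(0.80)/(239/365.25) = 0.341 per person-year. In Groups 1-3 it is -ln(1 - 0.2888)/(365/365.25) = 0.341. The crude percentages were 20.0% and 28.9%, so the artefact disappears.

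**4. Baseline N-positives.** Let s be the N-positive share and c the share of their infections found by PCR. Assume equal true risk whatever the serostatus, and full detection in N-negatives. The FAS percentage is then p × [(1 - s) + s × c]. The documents give neither s nor c. At p = 20% and c from 0 to 0.5:

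- s = 20%: between 0.20 × 0.80 = 16% and 0.20 × 0.90 = 18%.
- s = 80%: between 0.20 × 0.20 = 4% and 0.20 × 0.60 = 12%.

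The bracket is the same in expectation for every randomised group, so the 12-month to 8-month ratio stays at 1.44. Chance imbalance in s for 50 v 50 is ±1.96 × √(2s(1 - s)/50), which is ±16 points at s = 20% or 80% and ±20 points at s = 50%. At p = 20% and c = 0 this moves the FAS percentage by at most 0.20 × 19.6 = 3.9 points.

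**5. Crit11 beside item c.** Item c of Appendix 3 removes samples on or after infection confirmed by molecular testing or a non-S ELISA, whatever the baseline serostatus. Crit11 applies the N-ELISA rule only to participants negative on both assays at baseline. Crit13 removes data after infection but does not say in that place whether N conversion counts. If it does, S-positive, N-negative converters are removed and Crit11 is merely narrower than it needs to be. If Crit13 is programmed as PCR only, their post-infection samples stay in the PPI.

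**The case against.** The strongest reply is that no formal comparison depends on this table. The infection endpoints are exploratory, the protocol says infections are presented descriptively, no hypothesis is tested, and SAP 5.8.2 states that harm monitoring cannot be done without a placebo arm. Dose levels within Groups 1-3, or within Groups 4-6, share the same planned follow-up. All of that stands, and it sets the severity.

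Actual follow-up may also differ from plan. Participants who decline the booster may leave at about 6 months, and some followed other amendment versions. This makes the figures above illustrative, but it is also a reason to use person-time rather than a crude percentage. Table shells are in a separate specifications document that was not available, so a footnote or cut-off might appear there. The Day 240 serum sample is inferred from the visit type, because the assessment rows in protocol 1.3.2 show no column for that visit.

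A reader might infer three stronger things:

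- **That baseline seropositivity itself makes the schedules non-comparable.** It does not. PCR-positive participants are also counted, only N-positives (not everyone seropositive on S or N) are unable to convert, and 1:1:1:1:1:1 randomisation spreads them evenly in expectation.
- **That the infection objectives rest on this one percentage.** SAP 1.1 and 5.6 list molecularly confirmed COVID-19, N-protein conversion at selected timepoints and asymptomatic PCR positives separately.
- **That the primary immunogenicity set is contaminated.** Item c and the infection definition in 5.6 and 5.8.3 both include serology, so this follows only on a narrow reading of Crit13.

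The added sensitivity analysis on a 2-fold N-ELISA rise does not answer the point. It censors antibody data in the PPI and leaves the infection counts unchanged.

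**Conclusion.** The table as specified does not support a comparison of infection between Groups 1-3 and Groups 4-6. With equal, constant hazards, unequal follow-up alone would make Groups 1-3 look 1.31 to 1.51 times as infected, or 2.5 to 15.3 points higher, for Day 240 risks of 50% down to 5%. Those sizes rest on an assumed infection risk, a hazard unchanged by the booster, and planned follow-up being achieved. The difference in observation time itself is stated in the protocol.

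Under-counting of infection in baseline N-positives is real but concerns the level in all groups, and its size cannot be fixed from the documents. The mismatch between Crit11 and item c is a drafting gap with a consequence only on one reading. Severity is minor.

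**What to change.** In SAP 5.8.3:

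- Compare schedules over common windows: N conversion up to Day 71, the last serology day shared by all groups, and PCR-confirmed cases up to Day 184, before the booster. The central swab at the Day 184 visit in Groups 1-3 should not count towards that window.
- For full follow-up, give infections per person-time, split into primary and post-booster periods in Groups 1-3. State the date assigned to an N conversion, since it is known only to lie between two samples.
- Report N conversion among participants N-ELISA negative at baseline with at least one post-baseline N-ELISA result, whatever their S-ELISA, and report PCR-confirmed infection separately.

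In SAP 6.3, make Crit11 conditional on being N-ELISA negative at baseline, so that it agrees with item c however Crit13 is read.

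The cost is SAP wording and table programming on data already collected. The conversion table will have smaller denominators, and a few more samples may leave the PPI.
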